Protocol

Official Title: The Impact of Genetic and Environmental Factors on the Progression

of Chronic Pancreatitis: An Observational Study

NCT number: NCT04574297

Date: 30/9/2020

The Impacts of Genetic and Environmental Factors on the Progression of Chronic Pancreatitis

1 Background

Chronic pancreatitis (CP) is a chronic progressive disease and characterized by fibrosis and inflammation of the pancreas. The prevalence rates varied from 36 to 125 per 100 000 population in different countries.¹ Morphological changes, including atrophy, fibrosis, duct distortion and strictures, and calcification, etc., lead to the irreversible damage of pancreatic endocrine and exocrine functions. The loss of pancreatic functions indicates the progression of CP and leads to the poor quality of life and the increased medical resources utilization.¹

It has been well confirmed that environmental factors, including alcohol and smoking, were independent risk factors for the occurrence of CP.^{2, 3} These factors also accelerate the development from acute pancreatitis and recurrent acute pancreatitis to CP.⁴ Moreover, several studies explored the effect of alcohol and smoking on the progression of CP. Hao et al⁵ found that compared with idiopathic chronic pancreatitis (ICP), alcoholic chronic pancreatitis (ACP) usually had a more severe course, which confirmed the impact of alcohol on the progression of CP. Maisonneuve et al⁶ conducted a study with a cohort of 934 patients with ACP and found that tobacco smoking accelerated the appearance of calcification and diabetes independent of alcohol consumption. The impact of smoking was also found in patients with ICP.⁷ However, none of these studies considered the impact of genetic background on the progression of CP, which might be a potential mixed factor.

Over the past two decades, it has been increasingly appreciated that genetic factors also played an important role in the development of CP. The rare pathogenic variants in susceptibility genes of CP, such as *SPINK1* (encoding pancreatic secretory trypsin inhibitor), *PRSS1* (encoding cationic trypsinogen), *CTRC* (encoding chymotrypsin C) and *CFTR* (encoding cystic fibrosis transmembrane conductance regulator) genes, are overrepresented in both ICP and ACP, and related to earlier onset of CP.⁸⁻¹² However, few studies focused on the effect of genetic factors on the progression of CP. A prospective study conducted by Muller et al found that patients carrying *SPINK1* mutations had longer delay from onset of disease to pancreatic endocrine and exocrine insufficiency development. Another study by Frulloni et al also concluded exocrine and endocrine insufficiency occurred less frequently and later in CP patients with genetic mutations (*CFTR* and *SPINK1*) than those without. Onversely, Sun et al concluded that

CP patients carrying *SPINK1* c.194+2T>C mutation developed diabetes mellitus (DM) significantly since onset of CP.¹⁵ These discrepancies may be attributable to the small numbers of enrolled patients, the different racial backgrounds, and the analysis of limited genes and pathogenic variants. As far as we knew, there are no published studies investigating the influences of both environmental and genetic factors on the progression of CP.

2 Objectives

The study aims to investigate the comprehensive impact of both environmental and genetic factors on the progression of CP, defined as the development of either endocrine or exocrine insufficiency following the onset of CP.

3 Study setting

The study is designed as a prospective observational study and conducted in Changhai Hospital, which is a tertiary referral center and the largest CP medical center in China.

4 Eligibility criteria

Inclusion criteria

Consecutive patients with a diagnosis of CP and agreed to provide a blood sample for genetic tests are enrolled between January 2010 and December 2014.

Exclusion criteria

- 1) autoimmune pancreatitis;
- 2) pancreatic cancer diagnosed within two years following the onset of CP;
- 3) patient had less than two years' follow-up;
- 4) patients presenting with diabetes and/or steatorrhea at onset of CP.

5 Study design

If inclusion/exclusion criteria are met and written informed consent has been obtained, the patient will be enrolled in the present study and the following data are documented in detail: demographic data (date of birth, gender), alcohol consumption and smoking history, family history, age at disease onset, etiologies of CP, CP-related complications, laboratory and imaging results, and treatment.

All enrolled patients agreed to provide a blood sample for genetic tests. All known rare pathogenic variants of the *PRSS1*, *CFTR*, *SPINK1*, and *CTRC* genes are included in the final analysis. The detailed DNA preparation methods, gene sequencing, and pathogenic variants inclusion criteria have been described previously. Patients with at least one rare pathogenic variant are considered genetic factor/s

positive (denoted as G+).

Patients are considered smokers if they had smoked ≥ 100 cigarettes before the onset of CP. Additionally, based on their alcohol consumption patterns before the onset of CP, the patients are categorized into four groups, abstainers, light drinkers (≤ 20 g/d), moderate drinkers (≥ 20 g/d), and heavy drinkers (≥ 80 g/d). Patients with a history of either smoking or alcohol consumption are considered environmental factor/s positive (denoted as E+).

During follow-up, aside from visits owing to complaints of discomfort caused by CP, all patients will be periodically (annually at least) contacted for clinical and imaging (computed tomography or magnetic resonance imaging) check-ups. The examination results, any changes in alcohol consumption or smoking status, and CP complications are also recorded. Data for the present study will be obtained in 2020. The follow-up time is defined as the duration from the onset of CP (first clinical symptoms attributable to CP or first imaging procedure showing CP lesions) to the end of follow-up, last personal contact, diagnosis of pancreatic cancer, regional or total pancreatectomy, or death, whichever came first. All patients are prospectively observed from enrolment until the cessation of follow-up.

6 Outcomes

The primary endpoint is the development of pancreatic insufficiency (diabetes and/or steatorrhea). The components of the primary endpoint (diabetes and steatorrhea) are set as the secondary endpoints. Patients with diabetes and/or steatorrhea during the course of CP are considered to have pancreatic insufficiency. Diabetes is diagnosed according to the criteria of the American Diabetes Association, as follows: (1) hemoglobin A1C ≥6.5% (48 mmol/mol); or (2) fasting plasma glucose ≥126 mg/dL (7.0 mmol/L). Fasting is defined as no caloric intake for at least 8h; or (3) 2-h plasma glucose ≥200 mg/dL (11.1 mmol/L) during oral glucose tolerance test (OGTT), which is performed using a glucose load containing the equivalent of 75-g anhydrous glucose dissolved in water; or (4) in a patient with classic symptoms of hyperglycemia or hyperglycemic crisis, a random plasma glucose ≥200 mg/dL (11.1 mmol/L). Steatorrhea is diagnosed according to one of the following conditions: (1) chronic diarrhea with foul-smelling, oily bowel movements or (2) a positive result in a standard quantification test (fecal fat excretion of greater than 14 g/d). ¹⁶

7 Data management

Data collection

Clinical data regarding demographic data (date of birth, gender), alcohol consumption and smoking

history, family history, age at disease onset, etiologies of CP, CP-related complications, laboratory and imaging results, and treatment are collected during the first hospital admission

Statistical analysis

For continuous variables, tests of data normality are carried out using the Shapiro-Wilk test. Normally-distributed variables are presented as mean \pm standard deviation (SD) and compared using Student's t-test. And non-normally distributed data are presented as median (interquartile range, IQR) and compared using Mann-Whitney U test. Categorical variables results are presented as frequency and percentage. Chi-squared analysis or Fisher's exact test is used for comparison.

Cumulative incidence of pancreatic insufficiency after the onset of CP are presented by Kaplan-Meier survival curves. Log-rank test is further used to analyze the difference of cumulative rates of pancreatic insufficiency between two groups. *P* values for pairwise comparisons were adjusted using the Bonferroni correction. Cox proportional hazards regression model is used to identify the potential risk factors. Hazard ratios and 95% confidence intervals are calculated. All statistical tests are 2-sided. Data are analyzed using SPSS 23.0 (SPSS Inc, Chicago, IL) and SAS 9.4 (SAS Institute, Cary, NC).

8 Ethics approval

Ethical approval is obtained from Changhai Institutional Review Board with the ID of CHEC2020-142.

9 Funding

Support for this study come from the National Natural Science Foundation of China (Grant Nos. 81970560[[name]], 82070661 [[name]], 81873588[[name]]), Scientific Innovation Program of Shanghai Municipal Education Committee (No. 201901070007E00052[[name]]), and Clinical Research Plan of SHDC (SHDC2020CR2032B).

10 Declaration of interests

The authors declare that they have no competing interests.

11 References

- Singh VK, Yadav D, Garg PK. Diagnosis and Management of Chronic Pancreatitis: A Review.
 Jama 2019;322:2422-2434.

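### With no age criterion and E status fixed by exposure before onset, childhood-onset patients are almost all E-, and the unadjusted E and G/E comparisons do not separate exposure from age at onset

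*Combined protocol and SAP*

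**What the plan says.** **Population.** Protocol section 4 states: "Consecutive patients with a diagnosis of CP and agreed to provide a blood sample for genetic tests are enrolled", over the years 2010 to 2014. None of the four exclusions concerns age; the one tied to onset removes "patients presenting with diabetes and/or steatorrhea at onset of CP".

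**Exposure.** In section 5, "Patients are considered smokers if they had smoked ≥ 100 cigarettes before the onset of CP". For alcohol, "based on their alcohol consumption patterns before the onset of CP, the patients are categorized into four groups". A history of either habit makes a patient E+. The sentence that defines E+ does not repeat the pre-onset limit, but both classifications that feed it carry that limit. Later changes in smoking or drinking are recorded, and no rule reclassifies E from them.

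**Genetics and age.** Section 1 says of the rare pathogenic variants that they "are overrepresented in both ICP and ACP, and related to earlier onset of CP".

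**Analysis.** Section 7 and the separate SAP carry the same text: Kaplan-Meier curves from CP onset, log-rank tests, Bonferroni-adjusted pairwise comparisons, and a Cox model whose covariates are not named. Nothing stratifies, adjusts or restricts by age at onset, although it is collected ("family history, age at disease onset, etiologies of CP, CP-related complications", sections 5 and 7).

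**The concern.** The exposure window closes at CP onset, so its length depends on age at onset. A patient with onset at age 8 had practically no opportunity to become E+. The E- group therefore mixes unexposed adults with patients who could not have been exposed, while the E+ group is nearly all adult-onset. The E contrast is then partly a contrast between adult-onset and childhood-onset disease.

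The same holds for the joint question. The plan does not list the four groups formed by crossing G with E, but its two labels, its joint objective and its pairwise comparisons point to them. If carriers tend to have earlier onset, childhood-onset patients will tend to gather in G+E-, and a difference between that group and the others could come from genes, exposure or age at onset.

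At stake is the main objective in section 2, the combined effect of environment and genes on progression.

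**Working it through.** The documents give no sample size, event count, E+ prevalence, age distribution or hazard by age at onset. There is no planned figure to reproduce, and every input below is an assumption.

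**1. Crude hazard ratio when E has no effect**

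- *c*: share of the cohort with childhood onset, all E-.
- *p*: probability of E+ among adult-onset patients, taken as 0.5.
- *r*: hazard of insufficiency in childhood-onset relative to adult-onset patients.
- Childhood-onset share of E-: *w* = *c* / (*c* + (1 - *c*)(1 - *p*)).
- Initial crude E+ versus E- hazard ratio: 1 / ((1 - *w*) + *w r*).

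For *c* = 30%: *w* = 0.30 / (0.30 + 0.35) = 0.46. At *r* = 0.5 the ratio is 1 / (0.54 + 0.23) = 1.30.

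| *c* | *w* | *r* = 0.3 | *r* = 0.5 | *r* = 0.7 | *r* = 1.0 | *r* = 1.5 |
|---|---|---|---|---|---|---|
| 10% | 0.18 | 1.15 | 1.10 | 1.06 | 1.00 | 0.92 |
| 30% | 0.46 | 1.48 | 1.30 | 1.16 | 1.00 | 0.81 |
| 50% | 0.67 | 1.88 | 1.50 | 1.25 | 1.00 | 0.75 |

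Simulated Cox fits (adult hazard 4% per year, censoring at 5-15 years) agree. For *c* = 10-30% they give 1.17-1.55 at *r* = 0.3, 1.10-1.32 at 0.5 and 1.07-1.17 at 0.7. For *c* = 50% they reach about 1.95 at *r* = 0.3. At *r* = 1.5 the simulated values lie between about 0.75 and 0.94. When *r* < 1 the fitted value can exceed the initial ratio, because slower-progressing childhood-onset patients accumulate in the E- risk set.

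**2. Chance of a false finding, one illustration**

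Assume N = 1000, *c* = 20%, *r* = 0.5, 40% cumulative incidence in adult-onset patients and two-sided alpha 0.05. By Schoenfeld's formula, the chance is Φ(|ln HR| √(D q(1 - q)) - 1.96), with D events and E+ share q.

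- *p* = 0.4: HR 1.172, q = 0.32, D = 1000 × (0.32 × 0.40 + 0.68 × 0.349) = 365. The root term is 0.159 × √(365 × 0.32 × 0.68) = 1.42, so the chance is about 29%.
- *p* = 0.6: HR 1.238, q = 0.48, D = 1000 × (0.48 × 0.40 + 0.52 × 0.333) = 365. The root term is 0.214 × √(365 × 0.48 × 0.52) = 2.04, so the chance is about 53%.

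The nominal figure is 5%.

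**3. Which analyses remove the bias**

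A stratum with no E+ patients contributes nothing to a stratified log-rank test of E or to the E coefficient of a stratified Cox model. Stratification should therefore give the same E estimate as restriction to adult onset. Simulations with a true E hazard ratio of 1.0, *c* = 30% and a step in hazard between childhood and adult onset gave:

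| Analysis | *r* = 0.5 | *r* = 0.3 |
|---|---|---|
| Crude | 1.33 | 1.52 |
| Childhood-onset indicator | 1.02 | 0.99 |
| Adult onset only | 1.02 | 0.99 |
| Single linear age term | 1.16 | 1.23 |

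If the effect of age is truly log-linear, the linear term does remove the bias (0.99 in the *r* = 0.5 setting).

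**4. Interaction of G and E**

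If childhood onset made up 50% of G+ and 5% of G-, with no true effects, the initial crude E ratios at *r* = 0.5 would be 1.50 in G+ and 1 / (1 - 0.095 × 0.5) = 1.05 in G-. Their ratio, 1.50 / 1.05 = 1.43, is a spurious interaction; simulation gave about 1.45. A linear age term left about 1.25, and a childhood-onset indicator left about 1.0. The documents give neither share.

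**The case against.** Four objections have weight.

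- **Restriction is not the only remedy.** A reader might infer that, with no E+ patients at childhood ages, no covariate can repair the contrast and the population must be restricted. That is wrong: an indicator or strata give the same E estimate as restriction. Only a single linear term is unreliable. Restriction at a fixed age is also incomplete, since adolescents can reach 100 cigarettes and, among adults, pre-onset exposure still accumulates with age.
- **The direction is open.** A reader might infer that E will look falsely harmful. The documents do not say that childhood-onset disease progresses more slowly. Section 1 reports conflicting findings on progression even in carriers, and an appeal to diabetes risk rising with age rests on outside knowledge and says nothing about steatorrhea. This objection stands in full.
- **A greater distortion among carriers is not shown.** Section 1 supports only earlier onset in carriers, which may be an earlier adult onset. The 50% share used above is invented, so the interaction figures show what is possible, not what to expect.
- **The E+ sentence says only history.** If later exposure counted, a childhood-onset patient could become E+ and the link with age would weaken. The pre-onset reading is likelier, and the alternative would define E by data arising after time zero.

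It can also be said that this is merely an unnamed Cox covariate. That does not cover the Kaplan-Meier curves and log-rank tests, which are specified and unadjusted.

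**Conclusion.** The concern holds in this form. With no age limit and a pre-onset exposure window, age at onset is tied by construction to E and, by the plan's own background, to G. The specified curves and log-rank tests give biased E and G/E contrasts whenever age at onset affects progression.

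Size and direction are unknown. Under assumed childhood-onset shares of 10-50% and relative hazards of 0.3 to 1.5, with half of adult-onset patients E+, a true E hazard ratio of 1.0 would appear as roughly 0.75 to 1.95. At a relative hazard of 1 there is no bias; above 1, E would look protective. The conclusion rests on the pre-onset reading of E+ and on some childhood-onset patients being enrolled, which the criteria permit but do not quantify.

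**What to change.** Keep enrolment as it is and change the statistical analysis text in section 7 and the SAP:

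1. State that E is determined by exposure before CP onset.
2. Stratify the log-rank tests by prespecified bands of age at onset, one of them childhood onset, and show Kaplan-Meier curves by band or for the restricted population.
3. Include age at onset in every Cox model through those strata or a flexible term such as a spline, not a single linear term.
4. Report the E and G/E contrasts restricted to patients whose onset came at an age when exposure was possible, either as a sensitivity analysis or as the stated target population. Fix and justify the cut-off before the data are analysed.
5. Show the all-ages crude result beside it, and the number of patients by age band and G/E group.

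Age at onset is already collected, so no new data are needed. The cost is slightly less precision and a narrower statement of whom the E effect applies to. Childhood-onset patients carry practically no information on E, and under stratification they still contribute to the G comparison.

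### Incidence curves start at CP onset but patients enter only by attending in 2010–2014; one delayed-entry check would expose a possible bias in the curves, and less often in the hazard ratios

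*Combined protocol and SAP*

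**What the plan says.** Section 2 takes progression as the outcome, "defined as the development of either endocrine or exocrine insufficiency following the onset of CP". Section 5 sets the clock accordingly: "The follow-up time is defined as the duration from the onset of CP", where onset is the first attributable symptom or the first imaging that shows lesions. The statistics part of section 7 and the SAP then apply Kaplan-Meier, log-rank with Bonferroni adjustment, and Cox regression on that clock.

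Entry works differently. Section 3 describes a single hospital, "which is a tertiary referral center and the largest CP medical center in China". Section 4 takes consecutive CP patients who give blood and are "enrolled between January 2010 and December 2014", with no limit on how long ago onset was. Section 5 adds: "All patients are prospectively observed from enrolment until the cessation of follow-up".

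Two exclusions in section 4 bear on this. One removes "patients presenting with diabetes and/or steatorrhea at onset of CP", so later insufficiency is not a bar to entry. The other applies if the "patient had less than two years" of follow-up; by the definition in section 5 those two years run from onset, so the rule does not deal with late entry. Section 6 counts diabetes or steatorrhea at any point in the disease course.

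Neither the protocol nor the SAP names an entry time, a sensitivity analysis, a summary of the onset-to-enrolment gap, or a count of events before enrolment.

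**The concern.** A patient whose disease began years before 2010 is in the data only because he or she was alive and attended in the window. If becoming insufficient makes attendance more likely, patients with early events are over-sampled and the curves rise too fast. If it makes attendance less likely, or shortens life, the curves rise too slowly. The protocol gives one reason to take this seriously: section 1 says that loss of pancreatic function "leads to the poor quality of life and the increased medical resources utilization", and recruitment is through hospital attendance. That sentence gives no size and does not concern this hospital, so attendance here could equally fall.

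The cumulative incidence curves are most exposed, because selection acts directly on when sampled patients had their event. The exposure comparison is less exposed as long as the selection acts alike in both groups. Nothing in the planned output would show whether either has happened.

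**Working it through.** **Inputs.** The plan has no figure to reproduce: it gives no sample size, event rate, mortality, attendance rate or onset-to-enrolment gap. From the documents: clock from onset, entry 2010–2014, data cut 2020, insufficiency at onset excluded. Assumed: half the patients E+; insufficiency hazard 0.05/yr in E−; true HR 1.5, so 0.075/yr in E+; attendance 0.10/yr; mortality 0.01/yr (E−) and 0.02/yr (E+); onsets spread evenly over the 25, 10 or 5 years to end-2014; 1,000 patients for standard errors (SE).

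**Mechanism.** Let f(t) be the true density of time to insufficiency and w(t) the chance of enrolment given insufficiency at t. The sampled density is proportional to f(t)·w(t). If w does not vary with t within an exposure group it cancels and there is no bias, even if mortality differs by exposure.

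**Hand example.** Take E− patients with onset at the start of 2005, no deaths, and attendance doubled to 0.20/yr after insufficiency. The window covers years 5 to 10.
- Insufficient before year 5: w = 1 − exp(−0.20×5) = 0.632; contribution (1 − e^−0.25)×0.632 = 0.140.
- Insufficient at year 5+s within the window: w = 1 − exp(−1 + 0.1s); contribution (e^−0.25 − e^−0.5) − e^−1.25(e^0.25 − 1) = 0.172 − 0.081 = 0.091.
- Still free at year 10: w = 1 − exp(−0.10×5) = 0.393; contribution e^−0.5×0.393 = 0.239.

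Sampled 10-year risk = (0.140 + 0.091)/(0.140 + 0.091 + 0.239) = 49%, against a true 1 − e^−0.5 = 39.3%. Other onset dates dilute this.

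**Simulation over all onset dates** (2 million onsets per run). Triples are the 25/10/5-year spreads. Risk is E− 10-year risk (true 39.3%) for the first two and E− 5-year risk (true 1 − e^−0.25 = 22.1%) for the third.

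| Assumption | E− risk, % | Shift, SE | HR (true 1.50) |
|---|---|---|---|
| No dependence | 39.3/39.4/22.1 | about 0 | 1.50/1.50/1.50 |
| Attendance ×2, any attendance in the window | 47.1/45.4/26.3 | +3.5/+2.6/+2.1 | 1.45/1.48/1.49 |
| Attendance ×2, first-ever attendance in the window | 41.5/44.2/26.3 | +0.9/+2.1/+2.1 | 1.49/1.48/1.49 |
| Attendance ×1.5 | 44.1/42.8/24.4 | +2.1/+1.5/+1.2 | 1.47/1.49/1.50 |
| Attendance ×0.5 | 31.0/34.7/19.4 | −4.1/−2.1/−1.5 | 1.55/1.51/1.50 |
| Mortality ×3 after insufficiency | 36.5/38.9/22.0 | | 1.43/1.48/1.49 |
| Mortality ×3 and attendance ×2 | 44.0/44.8/26.1 | | 1.38/1.45/1.48 |
| Extreme mortality: E− 0.02 then 0.06/yr, E+ 0.06 then 0.18/yr | | | 1.32/1.42/1.47 |
| Attendance ×2 in E+ only | | | 1.82/1.81/1.73 |
| Attendance ×2 in E− only | | | 1.19/1.22/1.29 |

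The first-ever row reflects section 7, which has clinical data collected at the first hospital admission.

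**Group contrast.** The true E+ minus E− risk difference is (1 − e^−0.75) − (1 − e^−0.5) = 13.4 points at 10 years, and (1 − e^−0.375) − (1 − e^−0.25) = 9.2 at 5 years. With attendance ×2 (any attendance) it is 12.9/13.7/10.3 points, a shift of −0.15/+0.09/+0.39 SE. The HR shifts by −0.5/−0.2/−0.1 SE.

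**Events before enrolment.** With no dependence, 22% to 67% of events precede enrolment, depending on the spread.

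**Other inputs.** A second simulation used a 30-year spread, a baseline hazard of 0.04/yr and true HRs of 0.6, 1.5 and 2.5. Without dependence the 10-year curve was off by at most 1.2 points and the HR by at most 2%. In 102 scenarios with dependence, some of them extreme, the curve was off by −18.8 to +15.9 points (median absolute 3.8). The HR was off by a median of 3%, within 10% in 79% of scenarios, and by 28% at worst.

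**Delayed entry.** With entry at the later of enrolment and two years after onset, the HR returns to 1.49–1.50, and E− risk from year 2 to year 10 to 32.9–33.1% (true 1 − e^−0.4 = 33.0%), in all scenarios of the first set in which attendance does not rise before insufficiency.

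**The case against.** The stated aim is the impact of exposures, which is a contrast, and the contrast hardly moves under the main assumption. That stands; taken alone, the effect on the HR would be minor. The mechanism rests on one general sentence in the Background, and every rate used here is assumed. That stands too.

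The remedy also has a price. Delayed entry discards pre-enrolment events, and at an assumed 1,000 patients the onset-based HR has the lower mean squared error in 19 of 21 settings where attendance does not differ by exposure. Delayed entry does better in all 6 where it does differ. It also assumes that enrolment is unrelated to imminent insufficiency. If attendance triples in the year before insufficiency and doubles after, plain delayed entry gives 41.4/40.0/17.6% against a true 33.0/33.0/13.9%, no better than the onset-based 40.2/39.5/17.6%. This is why it can only be a check.

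A reader might infer three stronger things:
- That the status of insufficiency between onset and enrolment is undefined. No single sentence settles it. But the onset clock, an exclusion limited to insufficiency at onset, an endpoint that covers the whole disease course, and incidence counted from onset together make it an event.
- That this is the classical truncation error, in which only event-free patients can enter. It is not, because pre-enrolment events are counted.
- That the prospective label is misapplied. Section 5 itself limits prospective observation to the time after enrolment.

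What the objections leave standing is that the curves are a planned output and that nothing planned would reveal a selection effect.

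**Conclusion.** The point holds in conditional form, as a cheap improvement of minor to moderate weight. If neither attendance nor survival depends on insufficiency, there is no bias. If attendance doubles after insufficiency, the absolute curves are too high by about 0.9 to 3.5 SE at an assumed 1,000 patients, depending on the onset spread and on whether entry means the first-ever admission or any attendance in the window. If attendance falls or mortality rises, the curves are too low. With doubled attendance the HR stays at about 1.45–1.49 against 1.5. It moves materially mainly when attendance after insufficiency differs by exposure (about 1.2 to 1.8 against 1.5) or when mortality after insufficiency is very high.

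The documents do not support saying that the planned HRs are invalid, or that the curves are biased in a known direction. The actual onset-to-enrolment gap is not given, and the effect may be negligible. The calculations with the inputs listed concern E+ and E−; no conclusion is drawn about the G groups.

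**What to change.** Keep the onset-based analysis as primary; it matches the objective. Add to the SAP:

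> Insufficiency arising between CP onset and enrolment counts as an event and is ascertained retrospectively. The onset-to-enrolment gap (median, IQR) and the number and share of events before enrolment will be reported by G and E group. Sensitivity analysis: on the time-since-onset scale, each patient joins the risk set at the later of enrolment and two years after onset, if then free of insufficiency (left-truncated Kaplan-Meier; Cox with an entry time). Curves are conditional on freedom from insufficiency at two years and are shown beside the onset-based curve on the same condition.

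The two-year floor is there because the follow-up exclusion, counted from onset, makes inclusion depend on reaching two years. A repeat with entry at the later of 12 months after enrolment and two years after onset is optional. It gave 33.1/33.1/13.9% in the case above where plain delayed entry failed.

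The cost is SAP wording plus the enrolment date, which a cohort observed from enrolment should hold. Pre-enrolment events drop out of the check, and the SE of the log HR is about 1.2 to 2.2 times larger. For the E− curve from year 2, root mean squared error with attendance ×2 falls from 7.1/4.7/2.0 points (onset-based) to 4.8/2.9/1.8. With no dependence it rises from 2.2/2.3/1.6 to 4.3/2.8/1.7. The first two years after onset stay unchecked.
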